Research Protocol

Title: Ocular Sarcoidosis Open Label Trial of ACTHAR Gel

Principal Investigator: [name], DO

NCT Number: 02725177

Document Date: 05/14/2018

Investigator initiated study (IIS) Form

Principal Investigator: [name], DO

Institution and Department: Cleveland Clinic Respiratory Institute

Contact information: [name], DO
[name]
[name]
[name]

Date: May 14, 2018
Amendment 4

1. Title of Study:

Ocular Sarcoidosis Open Label Trial of ACTHAR Gel

2. Hypothesis:

Treatment with ACTHAR Gel will result in a reduction of ocular inflammation in patients with active ocular sarcoidosis that requires systemic immunosuppressant therapy

3. Rationale for the study:

The initial treatment of ocular sarcoidosis usually relies on a combination of topical glucocorticoids and oral glucocorticoids, both of which are associated with significant ocular and systemic toxicities. Steroid-sparing therapies are limited by variable and unpredictable efficacy, prolonged time until clinical response, medication intolerance, and difficulties obtaining payor approval. As a result, it is not uncommon that treating physicians must choose between excessive glucocorticoid toxicity versus poor control of ocular inflammation. Ongoing ocular inflammation, in turn, leads to eventual visual loss and occasionally blindness.

There is a need for a more reliable, expeditious therapy that can be used as an alternative to glucocorticoids in sarcoidosis uveitis. Adrenocorticotrophic hormone, through activation of melanocortin receptors on leukocytes, can dampen immune responses through non-glucocorticoid dependent mechanisms. The proposed study will aim to define whether there is effectiveness for ACTHAR gel in these patients, delineate an effect dosing regimen, and provide information about the safety of this approach for moderate to severe ocular sarcoidosis.

ACTHAR is a 39-amino acid peptide natural form of adrenocorticotropin hormone (ACTH) that was initially approved in 1952 by the FDA. It has since been approved for 19 indications including respiratory sarcoidosis, multiple sclerosis, and infantile spasms.

4. Patient Population and Estimated Sample Size:

Patients with sarcoidosis (as defined by ATS/ERS/WASOG criteria) who have moderate to severe ocular sarcoidosis, defined as:

1. Any posterior, intermediate or panuveitis of sufficient severity to warrant therapy, in the opinion of the treating physician –OR—
2. Anterior uveitis requiring 4 or more daily applications of topical corticosteroids to maintain control of inflammation.

We propose to enroll patients, at the Cleveland Clinic, until at least 20 patients have successfully completed 4 weeks of therapy in this open label trial in order to determine effect size, speed of response and tolerability. In the event the Cleveland Clinic is unsuccessful in recruiting a sufficient number of subjects additional sites may be added as needed.

Statistical Analysis: The proof of concept patient population will consist of patients with ocular sarcoidosis. The definition of condition improvement is such that the patients will be classified under any of the following:

- a) Improved visual acuity (by at least one grade)
- b) Resolution of intraocular inflammation (no more than trace cells)
- c) Tapering of ocular or oral steroids by at least 50%
- d) Reduction of cystoid macular edema (graded by the ophthalmologist)
- e) No worsening of any of the above

Given these conditions, the acceptance of a composite endpoint and an assumption that only 20% of those with intraocular sarcoidosis will spontaneously remit or improve on the composite endpoint in the time-frame of the study, inclusion of 20 patients confers an 87% power to identify a 50% response rate from the medication at a two-sided alpha error rate of 0.05

The Cleveland Clinic will oversee the study, and maintain responsibility for collection of the case report forms and analysis of the data.

Study Design:

Inclusion/Exclusion Criteria

Inclusion Criteria

- Patient with sarcoidosis as defined by ATS/ERS/WASOG guidelines
- Any posterior, intermediate or panuveitis of sufficient severity to warrant therapy, in the opinion of the treating physician --OR-- Anterior uveitis requiring 4 or more daily applications of topical corticosteroids to maintain control of inflammation, or uncontrolled with topical therapy
- Persistent disease activity (active uveitis) at the time of screening

Exclusion criteria

- Other cause for ocular inflammation
- Uncontrolled diabetes, hypertension, or other contra-indication to increased dosage of glucocorticoids

- Recent (less than 4 weeks) intra-ocular or intra-orbital steroid injection
- Escalation of immunosuppressive medications between screening and initiation of the study medication
- Severe extra-ocular sarcoidosis likely to require additional therapy (in the opinion of the investigator)
- Administration of an investigational medication for sarcoidosis within 3 months, or 5 half-lives, whichever is longer
- Have a history of any opportunistic infection within 6 months prior to screening
- Have any history of malignancy, except fully resected cutaneous squamous cell cancer or cutaneous basal cell cancer, or cervical carcinoma in-situ with a minimum of 5 years period without recurrence
- Severe other organ disease felt to be likely to lead to death within the next six months
- Unable to follow the study protocol, including the requisite travel and follow-up ocular testing
- Women of childbearing potential must be using adequate birth control measures (abstinence, hormonal contraceptives, intrauterine device, barrier method with spermicide, or surgical sterilization) and must agree to continue such precautions, and not become pregnant or plan a pregnancy for 6 months after receiving their last treatment with study agent. Women of childbearing potential must test negative on a serum pregnancy test at screening.
- Breastfeeding women are excluded from participation

Study Procedures

Baseline assessments:

- Ocular exam (including visual acuity, intraocular pressure, cell count, vitreous haze assessment); visual analogue assessment of vision
- Retinal angiography and optical coherence tomography; (if not performed within the previous 4 weeks).
- Sarcoidosis Health Questionnaire Ocular module (SHQO)
- Fatigue Assessment Scale (FAS)
- King's Sarcoidosis Health Questionnaire (KSHQ)
- Blood draw for biomarkers;
- Extra-ocular organ involvement (WASOG instrument)

Treatment with ACTHAR Gel for 24 weeks

- Initial treatment with 80 units daily for ten days (induction phase)
- Maintenance treatment with 80 units twice weekly (maintenance phase)
- In the event of substantial side-effects deemed to be probably related to ACTHAR gel by the investigator; the dose may be reduced to 40 units twice weekly in subjects who have controlled inflammation.
- If they are not showing any evidence of improvement after 4 weeks, then the medication will be discontinued and management will be at the discretion of the treating physician.

	Screen	Week 0	Week 2	Week 4	Week 6	Week 8	Week 12	Week 18	Week 24	Week 36	Week 48
Informed Consent	X										
Focused H&P	X	X		X		X	X	X	X	X	X

	Screen	Week 0	Week 2	Week 4	Week 6	Week 8	Week 12	Week 18	Week 24	Week 36	Week 48
Ophthalmologic exam	X	X	X	X	X	X	X	X	X	X	X
Intraocular pressure	X	X	X	X	X	X	X	X	X	X	X
Visual acuity (Snellen)	X	X	X	X	X	X	X	X	X	X	X
Retinal angiography		X		X			X		X		X
Optical coherence tomography		X		X			X		X		X
Assess organ involvement	X	X		X			X	X	X	X	X
QOL instruments (FAS, KSHQ, SHQO)		X		X		X	X		X		X
Toxicity assessment			X	X	X	X	X	X	X	X	X
Medication list	X	X	X	X	X	X	X	X	X	X	X
Dispense medication		X		X		X	X	X	X	X	
Inflammatory biomarkers (serum draw for freezing)		X		X		X	X	X	X		X
Patient stipend	X	X	X	X	X	X	X	X	X	X	X

Protocol for treatment failure

[figure not shown]
- Treatment failure will be defined as any of:
 - Two step increase from baseline in SUN activity (anterior chamber) grade on two consecutive readings, or increase from Grade 3 to Grade 4
 - Failure to demonstrate improvement by 12 weeks in subjects with baseline SUN Grade ≥ 2
 - Failure to demonstrate any improvement by week 24 in SUN Grade 0-1+
 - Significant worsening of vitritis, retinal vasculitis, or macular edema associated with reduction of visual acuity
 - No improvement of vitritis, retinal vasculitis, or macular edema by week 12 in subjects with more than trace vitreous cells
- In the event of worsening inflammation during prednisone tapering, the dose of prednisone will be increased to the last dose level for an additional 4 weeks, prior to resumption of the tapering schedule
- In the event of treatment failure prior to the prednisone tapering phase, or in the event that the subject requires a second prednisone escalation, the subject will be dropped from the trial, and management of uveitis will be at the discretion of the treating physician.

Criteria for drug interruption or discontinuation

- Uncontrolled hyperglycemia requiring hospitalization, leading to other complications, or unable to be controlled with anti-diabetic medications
- Vision-threatening elevation of intraocular pressure unable to manage with topical anti-glaucoma therapy
- Infections requiring hospitalization (medication may be resumed after the infection is

resolved)

- Other severe medical complications deemed to be likely associated with study medication in the opinion of the investigator

5. Primary end-point:

(Measured at 24 weeks):

Proportion of patients meeting the composite of improvement of any one of the following variables, with no worsening of any single one, and no need for additional sarcoidosis therapies:

- visual acuity
- resolution of intraocular inflammation
- tapering of ocular or oral steroids by at least 50%
- reduction of cystoid macular edema

6. Secondary end-points:

- Proportion of patients meeting the primary endpoint at 4, 8 and 12 weeks
- Toxicity (including intraocular pressure)

- Durability of effectiveness (out to 48 weeks)
- Quality of life
- Inflammatory biomarkers
- Extra-ocular organ activity

7. Estimated time line (including contracting, IRB approval, study initiation, enrollment, study completion and submission of publication):

Thirty-six months, including six months to complete contracting and protocol development, 24 months for patient recruitment and study, and six months for data analysis and manuscript submission

8. Adverse Events and Data Monitoring

The risks of ACTHAR include and are not limited to those seen with glucocorticoid use. Acthar Gel causes the release of endogenous cortisol from the adrenal gland. Therefore all the adverse effects known to occur with elevated cortisol may occur with Acthar Gel administration as well. Common adverse reactions include fluid retention, alteration in glucose tolerance, elevation in blood pressure, behavioral and mood changes, increased appetite and weight gain.

Substantial side effects related to ACTHAR gel could include infection requiring parenteral antibiotics or any opportunistic infection; diabetes that cannot be controlled with conventional therapy; fluid retention that cannot be controlled with conventional diuretics; mood or personality changes deemed in the opinion of the investigator to require dose reduction.

The subject will undergo a focused history and physical examination at nine study assessment dates. The appropriate laboratory and ocular studies will be obtained as per the timeline. The study coordinator will contact patients by phone during the induction period. Adverse events that take place during the testing or afterwards will be recorded along with the patient's data and will be reported directly to the IRB by the PI. A data monitor will be assigned to the study.

All tests are routinely performed here at the Cleveland Clinic. The risks of each procedure are minimal.

9. Ethical considerations

Recruitment

We propose to enroll patients, at the Cleveland Clinic, until at least 20 patients have successfully completed 4 weeks of therapy in this open label trial in order to determine effect size, speed of response and tolerability. In the event the Cleveland Clinic is unsuccessful in recruiting a sufficient number of subjects additional sites may be added as needed. These sites may include

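### The Statistical Analysis text counts absence of worsening as a response in its own right, while Section 5 makes it an extra requirement, and nothing says which definition governs

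*Combined protocol and SAP*

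**What the plan says.** The protocol defines response in two places.

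- **Section 4, Statistical Analysis.** "The definition of condition improvement is such that the patients will be classified under any of the following". Five items follow on one level: a) visual acuity, b) intraocular inflammation, c) steroid tapering, d) cystoid macular edema, and "e) No worsening of any of the above". The power statement comes straight after and refers back to these conditions. It assumes that "only 20% of those with intraocular sarcoidosis will spontaneously remit or improve on the composite endpoint" and gives 87% power for a 50% response rate with 20 patients at two-sided 0.05.
- **Section 5, Primary end-point, at 24 weeks.** "Proportion of patients meeting the composite of improvement of any one of the following variables, with no worsening of any single one". The same sentence adds that no further sarcoidosis treatment may be needed.

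Each text holds something the other lacks. The thresholds for visual acuity (one grade or more) and for inflammation (trace cells at most) appear only in Section 4. The 24-week time point and the condition on further treatment appear only in Section 5. Neither refers to the other.

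Section 6 reuses the definition for a secondary endpoint: "Proportion of patients meeting the primary endpoint at 4, 8 and 12 weeks".

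**The concern.** One text is an OR over five items. The other joins three requirements with AND. An analyst who follows the Statistical Analysis paragraph and one who follows Section 5 can report different response rates from the same Week 24 data, and the difference passes to the 4, 8 and 12 week endpoint.

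The trial is open label and has no control group, so evidence of effect comes from setting the observed proportion against 20%. That 20% describes patients who remit or improve without the drug; it does not describe patients who stay the same. If stable patients count as responders while the benchmark stays at 20%, a drug with no effect is more likely to look effective. Choosing between the definitions after open-label results are known would also weaken the finding, whichever was chosen.

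**Working it through.** **1. Who is classified differently.** Every Section 5 responder has no worsening and therefore meets item e), so the literal Section 4 list can only equal or exceed the Section 5 rate. The patients who differ are:

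| Patient at Week 24 | Section 4, literal | Section 5 |
|---|---|---|
| Improved on one component, none worse, no further treatment needed | Responder | Responder |
| Unchanged on every component | Responder, by e) | Not a responder |
| Meets one of a) to d), worse on another | Responder, by the item met | Not a responder |
| Meets one of a) to d), none worse, further sarcoidosis treatment needed | Responder | Not a responder |

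**2. What other text suggests was meant.** The 20% assumption speaks of remission or improvement. The treatment section says: "If they are not showing any evidence of improvement after 4 weeks, then the medication will be discontinued". The treatment-failure section lists "Failure to demonstrate any improvement by week 24 in SUN Grade 0-1" (the 0 to 1+ range), so a patient in that range who is unchanged at Week 24 is a treatment failure there and improved under item e). These are management rules and do not set the responder definition. With the wording of the 20%, they suggest that e) is an AND condition placed in an OR list.

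**3. Reproducing the stated power.** Inputs from Section 4: n = 20, p0 = 0.20, p1 = 0.50, two-sided 0.05. No cut-off is stated. With P(X ≥ r) = Σ C(20,k) p^k (1−p)^(20−k), summed over k = r to 20:

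- P(X ≥ 8 | 0.50) = 0.8684, which matches 87%.
- P(X ≥ 8 | 0.20) = 0.0321.
- Two-sided exact p at 8 = 0.0321 + P(X = 0) = 0.0321 + 0.0115 = 0.0437 (from unrounded terms), below 0.05.
- P(X ≥ 9 | 0.50) = 0.7483, which does not match.

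So the cut-off is inferred to be 8 of 20. The normal approximation with null variance agrees: Φ[(√20 × 0.30 − 1.96 × √(0.20 × 0.80)) / √(0.50 × 0.50)] = Φ(1.115) = 0.868. The arithmetic of the power statement is sound.

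**4. Sensitivity to the definition.** Let f be the share of the 80% not expected to improve whom the literal list would still count. The no-effect rate is then 0.20 + f × 0.80. The documents give no value for f; the values below are assumptions.

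| Assumed f | No-effect rate | P(X ≥ 8 of 20) | P(X ≥ 9 of 20) |
|---|---|---|---|
| 0 (Section 5, 20% set for it) | 0.20 | 3.2% | 1.0% |
| 0.10 | 0.20 + 0.08 = 0.28 | 17.1% | 7.8% |
| 0.25 | 0.20 + 0.20 = 0.40 | 58.4% | 40.4% |

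The stricter cut-off of 9 reduces the inflation but does not remove it, and power at 50% falls to 74.8%.

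**The case against.** The strongest reply is that this is a drafting slip and the intended rule is plain. Section 5 alone is headed as the primary end-point, alone gives an assessment week, and is what Section 6 refers back to. The literal Section 4 list nearly defeats itself: if e) suffices, items a) to d) matter only for patients who improve on one component and worsen on another. The inflation figures need the reading that is probably unintended, assumed no-effect rates and an inferred cut-off. They also leave out the stopping and drop-out rules, which may leave fewer never-improved patients to be counted at Week 24. Finally, enrolment runs until at least 20 patients complete 4 weeks, so the Week 24 denominator need not be exactly 20.

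Most of this stands. Section 5 is probably the intended definition, and the figures show sensitivity; they do not estimate an error rate for this trial. The stopping rules could shrink the effect, but the plan does not say how stopped patients are classified, so the amount is unknown.

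It does not remove the conflict. The contradictory list sits in the paragraph labelled as the statistical analysis, and the 20%, 50% and 87% are tied to it. Nor can that list simply be ignored, because two of the improvement thresholds appear only there. Intent has to be inferred, and a primary endpoint should not depend on inference.

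**Conclusion.** The concern holds. The two definitions contradict each other, no text gives precedence, and the Section 4 list as written would count stable, mixed and additionally treated patients as responders. That the literal list gives an equal or higher response rate follows from the definitions alone.

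The size depends on which reading is used. Under Section 5, if 20% and 50% were set for that definition, there is no inflation and 20 analysed patients give 86.8% power. Under the literal list tested against 20%, the chance of a false positive result would rise from 3.2% to 17.1% or 58.4% if 1 in 10 or 1 in 4 of the other patients were also counted. Those shares and the cut-off of 8 of 20 are not in the documents. Because this is the primary responder definition of a small uncontrolled trial, it should be settled before the responder analysis is run.

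**What to change.** 1. In Section 4, take e) out of the any-of list. Define a responder as a patient who meets at least one of a) to d), AND has not worsened on any of them, AND has needed no additional sarcoidosis treatment.
2. State that this Section 5 definition governs the primary analysis at Week 24 and the same endpoint at 4, 8 and 12 weeks.
3. Carry the Section 4 thresholds for visual acuity and inflammation into Section 5, so that one text is complete.
4. Confirm that the 20% and 50% rates were set for this definition. If they were not, re-justify them and recompute the power.

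It would also help to say what counts as worsening on each component, since neither definition gives a threshold; the finding does not rest on this. No change to the treatment, stopping or failure rules is proposed.

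The cost is a few sentences and a check on the basis of two rates. If the rates are confirmed, the target of 20 patients and the 86.8% power are unchanged. The price is that the observed response rate may be lower than under the lenient list.

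### The treatment-failure rule removes subjects from the trial, not only from the drug, so their scheduled follow-up to week 48 ends and the plan does not say how they are counted

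*Combined protocol and SAP*

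**What the plan says.** The removal rule is in Protocol for treatment failure. Its condition reads "In the event of treatment failure prior to the prednisone tapering phase, or in the event that the subject requires a second prednisone escalation", and its consequence is "the subject will be dropped from the trial, and management of uveitis will be at the discretion of the treating physician".

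Three neighbouring rules are worded differently:

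- The same section deals with a first worsening in the taper: "In the event of worsening inflammation during prednisone tapering, the dose of prednisone will be increased to the last dose level". The taper then resumes, and nothing is said about leaving.
- The treatment part of Study Procedures covers early non-response: "If they are not showing any evidence of improvement after 4 weeks, then the medication will be discontinued". Care passes to the treating physician, but the text does not say that the subject leaves the trial.
- Toxicity is covered under "Criteria for drug interruption or discontinuation". As its title says, that section concerns the drug.

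The visit schedule runs to week 48. Section 6 lists as secondary endpoints durability to week 48, toxicity including intraocular pressure, quality of life, inflammatory biomarkers and extra-ocular organ activity. Section 8 says that adverse events arising at or after testing are recorded. It gives no duration and does not mention removed subjects.

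The available text has no early-termination visit, no follow-up of removed subjects, and no rule for counting them at week 24 or week 48.

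**The concern.** Removal depends on outcome. The failure criteria are ocular worsening or lack of improvement, and several act at week 12 or earlier. A subject who meets them before the taper has no further study visits on a plain reading, so the missing data are informative by design.

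Two things are at stake. The first is information: scheduled pressure checks, toxicity assessments, quality-of-life scores and biomarker samples that are never taken cannot be recovered by any analysis rule. The second is the durability figure, whose meaning depends on a denominator that the plan does not give. Section 3 names safety information as one of the study's aims, so the first loss matters even in a small open-label trial.

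**Working it through.** **1. The plan's own figure.** Section 4 gives a null response rate of 20%, a target of 50%, 20 patients, two-sided alpha 0.05 and 87% power. With the normal approximation for one proportion:

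Φ{[(0.50 − 0.20)√20 − 1.96√(0.20 × 0.80)] / √(0.50 × 0.50)} = Φ{(1.342 − 0.784)/0.5} = Φ(1.115) = 0.868.

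The exact binomial rule of 8 or more responders in 20 also gives power 0.868, with upper-tail error 0.032. The figure reproduces. The present point does not touch it, provided that removed subjects count as non-responders at week 24. The primary endpoint bars a need for additional sarcoidosis therapy, which points that way, but the plan does not state the rule.

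**2. The exit rules side by side.**

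| Situation | What stops | Does the text say the subject leaves the trial? |
|---|---|---|
| Failure before the taper | Trial participation | Yes |
| Second prednisone escalation | Trial participation | Yes |
| First worsening in the taper | Nothing | No |
| No improvement at week 4 | Medication | No |
| Listed toxicity | Medication | No |

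A week-4 non-improver could later meet a week-12 failure criterion. The text does not say whether that subject is still being followed by then.

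**3. What removal costs in visits.** Toxicity is scheduled at weeks 2, 4, 6, 8, 12, 18, 24, 36 and 48, which is nine assessments. A subject removed at the week-12 visit, with the taper not yet begun, loses:

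- weeks 18, 24, 36 and 48 for toxicity, intraocular pressure, acuity and ophthalmologic exam (4 of the 9 toxicity assessments);
- weeks 24 and 48 for quality of life;
- weeks 18, 24 and 48 for biomarkers.

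**4. Durability.** Assumed: 20 treated, d removed, and 70% of those retained still improved at week 48. The proportion of all treated is 0.70 × (20 − d)/20:

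- d = 4: 0.70 × 16/20 = 56%
- d = 6: 0.70 × 14/20 = 49%
- d = 8: 0.70 × 12/20 = 42%

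The reported figure is 70% in each case if retained subjects are the denominator. No extra data are needed for the all-treated figure, because a removed failure is already known not to be durable.

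**5. Late toxicity.** Assumed: a 10% risk of some late event, equal in retained and removed subjects. With m subjects followed, the chance of seeing at least one case is 1 − 0.9^m. If none is seen, the one-sided 95% upper bound is 1 − 0.05^(1/m).

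| Followed (m) | Chance of at least one case | Upper bound if none seen |
|---|---|---|
| 20 | 88% | 14% |
| 14 | 77% | 19% |
| 10 | 65% | 26% |
| 4 | 34% | 53% |

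The row for 14 matches d = 6. The rows for 10 and 4 are extremes: every week-24 non-responder removed, at the plan's 50% and 20% response rates. This table shows lost information. It does not show bias in either direction.

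**The case against.** Several stronger readings are tempting, and the documents do not support them.

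- *Late results come only from patients who did well.* Removal is limited to failure before the taper or a second escalation. A subject with one worsening during the taper stays, and subjects stopped for toxicity are not said to leave.
- *Toxicity after removal is not captured at all.* Section 8 provides for recording adverse events after testing. What is lost is scheduled assessment. Without a stated duration or any mention of removed subjects, that sentence does not replace planned pressure checks.
- *Toxicity will look better than it is.* The direction is not shown. Removed subjects may have had less drug, while retained subjects can have up to 24 weeks of it, so the retained group could look worse.
- *Durability data are lost.* The gap is an unstated denominator. Durability among responders is also a fair question in its own right, and the plan does not say that retained subjects would be the denominator.

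The other side can add that these are secondary endpoints in a 20-patient proof-of-concept study, and that events after removal are mixed with other therapy. Both are true. The first limits the severity of the point. The second is a reason to report by period, not a reason to stop collecting.

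The figure in the treatment-failure section was not visible in the text available, so the timing of the taper, and with it the number of subjects the rule would reach, could not be checked.

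**Conclusion.** The point holds in limited form. The protocol states a removal rule that ends scheduled follow-up for subjects selected by poor outcome, while its week-4 and toxicity rules stop only the drug. These passages need to be reconciled on follow-up. The week-48 safety, quality-of-life and biomarker results would come from a group from which defined failures have been removed.

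The size cannot be fixed from the documents, because the number removed is unknown. Under the assumptions above, a 70% durability figure corresponds to 42% to 56% of all treated for 8 down to 4 removals, and only if retained subjects are the denominator. The 20 treated is itself an assumption: enrolment continues until at least 20 complete 4 weeks, so more may be dosed. The primary endpoint and the 87% power are unaffected if removed subjects count as non-responders. This should be changed, but it does not undermine the trial's main result.

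**What to change.** Leave the clinical rules as they are and change only what follows them for data collection.

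- In Protocol for treatment failure, replace removal from the trial with wording that separates leaving study treatment from leaving follow-up. Apply the same follow-up wording to the week-4 rule.
- Keep subjects who still consent in the already scheduled safety and outcome visits to week 48, under whatever care their physician chooses.
- State that subjects meeting the removal rule by week 24 count as non-responders for the primary endpoint.
- In section 6, define durability over all dosed patients with failures counted as not durable. Durability among responders may be added as a supplement.
- Report toxicity for all dosed patients, split into on-drug and off-drug periods.

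The cost is a wording change plus visits and stipends that are already planned but would otherwise lapse. Late events in subjects off the drug may be mixed with effects of other therapy; the split by period makes that visible but does not remove it.

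### Section 5 does not exclude an acuity gain that follows a non-sarcoidosis eye procedure, and leaves treatment given for macular edema ambiguous

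*Combined protocol and SAP*

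**What the plan says.** Section 5 (Primary end-point) is "Measured at 24 weeks". A patient responds by improving on any one of acuity, intraocular inflammation, steroid dose or cystoid macular edema, "with no worsening of any single one, and no need for additional sarcoidosis therapies". No definition of additional sarcoidosis therapies appears in the text.

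The Statistical Analysis paragraph of Section 4 describes the two components at issue as "Improved visual acuity (by at least one grade") and "Reduction of cystoid macular edema (graded by the ophthalmologist"). Neither has to be attributed to the study drug. The list in that paragraph carries no condition on concurrent treatment.

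Eye injections appear once, as an entry exclusion limited to steroid: "Recent (less than 4 weeks) intra-ocular or intra-orbital steroid injection". The visit schedule has a row "Medication list" at every visit but no row for eye procedures. The Protocol for treatment failure includes "Significant worsening of vitritis, retinal vasculitis, or macular edema associated with reduction of visual acuity", so macular edema is handled as part of the disease.

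The power statement in Section 4 compares a 50% response rate with an assumption that "only 20% of those with intraocular sarcoidosis will spontaneously remit or improve on the composite endpoint". Section 6 reuses the primary endpoint at Weeks 4, 8 and 12.

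**The concern.** Acuity and macular edema can both change for reasons unrelated to the study drug. A patient whose cataract is removed between Week 0 and Week 24 may gain a grade of acuity with no change in the uveitis. In a randomized trial such events would tend to occur in both arms. Here the trial is open label, no comparator arm is described, and the benchmark is framed as spontaneous improvement, so nothing in the design offsets them.

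With about 20 patients, one or two misattributed responses could decide whether the result looks positive. The endpoint is also open to inconsistent scoring. Two assessors could class an injection for edema differently, one as added sarcoidosis therapy and the other as separate eye care, and each could defend the choice from the text.

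**Working it through.** **Step 1. Apply the rule to cases.**

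| Event between Week 0 and Week 24 | Additional-therapy clause | No-worsening clause | Result as worded |
|---|---|---|---|
| Acuity gain after cataract or capsule surgery, other variables stable | Not a sarcoidosis therapy in ordinary usage | Not triggered, since nothing worsened | Not excluded; responder on acuity alone |
| Edema or acuity gain after injection, laser or medication given for edema | Unclear: the term is undefined, but edema is treated as disease activity | Not triggered | Ambiguous; may already be excluded |
| Procedure followed by worse acuity, inflammation or edema | Depends on any treatment added | Triggered | Non-responder |

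The first row is a clear gap, the second an ambiguity. The third shows that a procedure can also move a patient the other way.

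**Step 2. Reproduce the plan's power.** Inputs from Section 4: n = 20, null rate 0.20, target rate 0.50, two-sided alpha 0.05. The plan states no success rule. The exact two-sided binomial test, summing outcomes no more likely than the one observed, rejects at 0 or at 8 or more responders.

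- P(X ≥ 8 | n = 20, p = 0.20) = 0.0321; adding the lower tail gives a two-sided size of 0.0437.
- P(X ≥ 8 | n = 20, p = 0.50) = 0.8684.
- Normal approximation: Φ[(0.30 − 1.96 × √(0.16/20)) / √(0.25/20)] = 0.8676.

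Both round to the stated 87%, so 8 of 20 is a reasonable inferred rule. An equal-tailed exact test (0.025 per side) would need 9 of 20 and has power 0.748, which does not match.

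**Step 3. Effect on the response rate.** One patient is 1/20 = 5 percentage points. This is a maximum, because a patient who would have responded by another route adds nothing.

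**Step 4. Effect on the false-positive chance, drug inactive.** The number of such patients is an assumption throughout.

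If k of 20 are certain responders and the rest respond at 20%, the chance is P(X ≥ 8 − k | n = 20 − k, p = 0.20):

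- k = 0: 0.032
- k = 1: 0.068
- k = 2: 0.133
- k = 3: 0.242

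A milder version converts a fraction q of would-be non-responders, giving a null rate of 0.20 + 0.80q:

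- q = 0.025: rate 0.22, chance 0.054
- q = 0.05: rate 0.24, chance 0.084
- q = 0.10: rate 0.28, chance 0.171

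Under a 9-of-20 rule, one certain responder moves the chance from 0.010 to 0.023.

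**Step 5. Upper bound on the power cost of a scoring rule.** If k affected patients were all forced to be non-responders and the others respond at 50%, power is P(X ≥ 8 | n = 20 − k, p = 0.50):

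- k = 0: 0.868
- k = 1: 0.820
- k = 2: 0.760
- k = 3: 0.685

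**The case against.** The strongest reply is that the existing wording already covers much of this. Other causes of ocular inflammation are excluded at entry. Edema is an endpoint component, and its worsening, or its failure to improve by Week 12 in patients with more than trace vitreous cells, can be treatment failure. New treatment for edema in such a patient is naturally read as additional sarcoidosis therapy. That stands, and it confines the clear gap to procedures such as cataract or capsule surgery. It does not remove the ambiguity, because the term is undefined.

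Second, Section 5 also requires no worsening of any variable. That is a real safeguard, but it does not catch a patient whom a procedure improved.

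Third, patients with no evidence of improvement after 4 weeks stop the drug, and further failure rules apply later. Many patients still treated at Week 24 will therefore already have improved, and a procedure need not change their classification. This reduces the likely effect. It does not close the gap, because the plan does not say how stopped or dropped patients are scored at Week 24.

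Fourth, an ophthalmologic exam and medication list at every visit would probably bring procedures to light. Without a rule fixed in advance, however, their handling would be decided with outcomes known in an unblinded study.

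Finally, the treatment-failure figure and some passages were not available for this review, so absence is judged on the visible text.

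**Conclusion.** The point holds in a limited form: a false route to response exists for acuity gained after a non-sarcoidosis procedure, and the scoring of treatment given for edema is unclear. The inflation is at most 5 points per affected patient at n = 20. The total is unknown because the documents give no procedure frequency. The rise from 3.2% to 6.8% is an illustration that assumes an inactive drug, the inferred 8-of-20 rule, and one patient who responds with certainty and meets both Section 5 conditions.

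A reader might infer more, and the documents do not support it:

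- They do not show that every patient treated for edema counts as a responder, since such treatment may already be ruled out.
- They do not show that bias can only favor the drug, since a procedure may be followed by worsening that turns a true responder into a non-responder.
- They give no basis for expecting two or three certain responders, so 13.3% and 24.2% are worst-case illustrations.
- The 87% power figure is not in error; it reproduces.

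The plan should be amended, because the repair is cheap.

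**What to change.** In Section 5, add a definition and a scoring rule:

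- New treatment given for macular edema counts as additional sarcoidosis therapy.
- An improvement in acuity or macular edema in an eye that had intraocular surgery, laser, or an intravitreal or periocular injection between Week 0 and the assessment does not count towards the patient's response.
- The patient may still qualify through improvement in the other eye, resolved inflammation or steroid tapering, subject to the two existing conditions.

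The endpoint is per patient and no study eye is defined, so the rule has to discount the gain in the treated eye and then return to the patient level, as above. Apply it also at Weeks 4, 8 and 12, and record eye procedures (date, eye, type, reason) with the medication list at each visit.

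The cost is a short addition to Section 5 and one line on an existing form. The response rate may be slightly lower. The loss of power should be smaller than the Step 5 bound (86.8% to 82.0% for one affected patient) where the other routes to response stay open. Only scoring changes; clinical care is not restricted.
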